7.7 Data Collection Procedures for Patients Who Re-enroll in the Registry

For patients who re-enroll in the registry, registry physicians will document any hospitalizations, surgeries, and any adverse event of interests as defined in Section 7.1.2. The physician will assess and record the date of onset (where known) and description of the event. These events will be reported via eCRF from the time of initial registry discontinuation through the date of re-enrollment, irrespective of any treatment interruption, any changes in treatment, or discontinuation of adalimumab.

The use of other medications used to treat CD and the stop and the restart dates for Humira, as applicable, from the time of initial registry discontinuation through the date of re-enrollment will be collected.

Effectiveness data will not be collected during the timeframe when the patient was not participating in the registry.

For visits occurring after re-enrollment, registry physicians will resume data collection in the eCRF process as outlined in the protocol. The duration of follow-up includes the time from initial registry consent up to 6 years.

7.8 Data Collection Procedures for Patients Who Participate in the Direct to HCP Process

For patients participating in the direct to HCP process, HCPs will document any hospitalizations or surgeries and any adverse event of interest as defined in Section 7.1.2 annually via a paper questionnaire or EDC. The HCP will assess and record the date of onset (where known), and description of the event. The use of other medications used to treat CD, and the start and stop dates for Humira will be collected on an annual basis.

These events will be reported to AbbVie from the time of initial registry consent up to 6 years, irrespective of any treatment interruption, any changes in treatment, or discontinuation of adalimumab.

Effectiveness data will not be collected as part of the direct to HCP process.

8.0 Ethics and Quality

Prior to any registry-related data being collected, the informed consent statement will be reviewed and signed and dated by the patient and the person who administered the informed consent. A copy of the signed informed consent form will be given to the patient and the original will be placed in the patient's medical record. A patient informed consent template will be provided to the registry physician. A copy of the patient signed informed consent or data release form (as applicable) will be provided to the HCP.

8.1 Independent Ethics Committee (IEC) or Institutional Review Board (IRB)

Should the institution/affiliation require an institutional review board approval/notification of this protocol (and related informed consent), it shall be the physician's responsibility to secure such approval prior to initiating any study procedures.

8.2 Quality Assurance

Prior to the initiation of the study, an Investigator's meeting will be held with AbbVie personnel, the investigators and their study coordinators, the Registrat's project manager and the CRAs for the study. This meeting will include a detailed discussion of the protocol, performance of study procedures and paper and eCRF completion. In addition to or instead of the Investigator's meeting, the personnel at each registry site may be trained on the study procedures by a CRA at a study initiation visit via the telephone or on-site and will be given a paper and eCRF completion workbook for reference.

Approximately ten percent (10%) of the registry sites will be monitored on-site for the study. At each site selected for a visit, one hundred percent (100%) source document review for SAEs, adverse events of interest and dose interruption data will be performed against entries on the paper and eCRF and a quality assurance check will be performed to ensure that the physician is complying with the protocol and local regulations. The monitoring plan will detail how sites will be selected for the on-site monitoring visits. Throughout the study, Registrat-MAPI and AbbVie will periodically follow-up with the sites to ensure that SAEs and adverse events of interest are being reported.

All registry data will be entered in the study via the eCRF and the fax scan of paper PRO (Patient Reported Outcome) forms. All eCRF information will be imported directly into the electronic data capture system. Paper PRO forms are first quality controlled checked and then entered into the electronic data capture system. All other paper questionnaires (e.g., direct to HCP questionnaire) will be entered into the database on an annual basis. Any necessary corrections will be made to the database and documented via addenda, queries, source data clarification form or audit trail. A manual review of selected line listings will also be performed at the end of the study.

9.0 Source Documents and Case Report Form Completion

9.1 Source Documents

Source documents are defined as original documents, data and records. This may include hospital records, clinical and office charts, laboratory data/information, pharmacy dispensing and other records, recorded data from automated instruments, microfiches, photographic negatives, microfilm or magnetic media, and/or x-rays. Data collected during this study must be recorded on the appropriate source documents. The only exception will be for patient-completed questionnaires (SIBDQ and WPAI). There will be no corresponding source documentation as the subject completes the forms directly on the CRF.

The Registry Physician(s)/institution(s) will permit study-related monitoring, audits, IEC/IRB review, and regulatory inspection(s), providing direct access to source data documents.

9.2 Case Report Forms

All data associated with this registry will be collected and reported electronically (eCRF) via a web address and secure password. Patient self-administered questionnaires will be completed on paper forms and then submitted to be entered into the database.

At the Enrollment visit, the physician will complete the Enrollment eCRFs by obtaining and recording all available required information, as outlined in Section 6.4.

At subsequent visits corresponding to the schedule of assessment (Table 1), the physician will complete the appropriate eCRF by obtaining and recording all available information. Since this is an observational registry conforming to usual clinical practice, data from patient visits that most closely correspond to the recommended schedule of assessment at Months 3, 6, 9, 12, 18, 24, and every 6 months through the end of registry participation will be collected.

Paper questionnaires will be generated for patients that decline re-enrollment to participation in the Registry or who have discontinued from the Registry for other reasons, and consent to data release for the completion of a simplified HCP questionnaire in the direct to HCP process. Completed questionnaires will be entered into the database on an annual basis.

Upon completion of or termination from the registry, all patients should have study completion eCRFs completed as well as an assessment of their current medical conditions.

10.0 Statistical Methods and Determination of Sample Size

10.1 Statistical and Analytical Plans

Analyzable Populations:

Safety Populations During the Registry:

The Registry Safety Population consists of all patients who received at least one dose of Humira (adalimumab) in the Registry. This will be the population for safety analyses in the Registry and include safety data collected during the Registry only.

The "Episodic Dosing" Population will consist of patients in the Registry Safety Population who:

- discontinue Humira (adalimumab) at least once for more than 70 days and receive at least one dose of adalimumab after the treatment interruption,
- do not receive any other biologics during the treatment interruption and,
- provide data before and after Humira (adalimumab) treatment interruption period(s)
- and include safety data collected during the Registry only.

For patients previously treated with commercial Humira before enrollment into the Registry, Day 1 of adalimumab treatment will be the 1st day of Humira therapy, i.e., before enrollment into the Registry. Detailed information on concomitant medications, safety and effectiveness between the 1st dose of Humir and enrollment into the Registry will be available for these patients.

Re-enrollment Safety Population:

The Re-enrollment Safety Population consists of all patients who were discontinued from the Registry due to prior protocol withdrawal criteria (i.e., patients who have discontinued Humira therapy) or discontinued for other reasons and re-consent to participation in the Registry. This will be the population for safety analyses of data collected during the re-enrollment period.

For patients that re-enroll in the Registry, safety information collected between registry discontinuation and re-enrollment based on a retrospective review of their patient records will be analyzed separately.

HCP Safety Population:

The HCP Safety Population consists of all patients that decline re-enrollment to participation in the Registry or who have discontinued from the Registry for other reasons and consent to data release for the completion of a simplified HCP questionnaire in the direct to HCP process. This will be the population for safety analyses of data collected on HCP questionnaire.

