- For patients that decline re-enrollment for full safety and effectiveness data collection or who have discontinued from the Registry for other reasons, physicians will be asked to obtain the patient's consent to data release for the completion of a simplified Healthcare Provider (HCP) questionnaire on an annual basis. The first data collection period will capture data from the time of patient's discontinuation of the Registry through the start of the direct to HCP process. The questionnaire focuses on the collection of surgeries or hospitalizations and adverse events of special interest and Crohn's related medication use since registry discontinuation. The questionnaire may be completed by the registry physician or the patient's current HCP (if they are no longer under the care of a registry physician). An HCP is not considered a participating investigator in the registry since they are only completing an annual questionnaire on behalf of a former registry patient. Participating registry investigators for which all of their patients have discontinued from registry participation may convert to an HCP status if their patients(s) choose to participate in the HCP process.

If treatment with Humira is permanently discontinued for any reason, patients will be encouraged to remain in the registry or to participate in the direct to HCP process unless consent is withdrawn.

When applicable, information about the effectiveness of Humira therapy will be provided by the patients and their physician. Effectiveness of therapy provided by the patient will be collected with PROs beginning with the registry enrollment visit, at regularly scheduled visits which are closest to Months 3, 6, 9, 12, and every 6 months thereafter, if part of routine clinical assessment. The following PROs will be used: Short Inflammatory Bowel Disease Questionnaire (SIBDQ), Health Care Resource Utilization (Unscheduled Outpatient Visits, Emergency Room Visits and Hospitalizations Questionnaire), and Work Productivity and Activity Impairment (WPAI). There are approximately 20 questions in the PRO assessments and it is expected that it will take approximately 15 minutes to complete them. Effectiveness of therapy will be collected through the Physician's Global Assessment beginning with the Registry enrollment visit and at regularly scheduled visits which are closest to Months 3, 6, 9, 12, and every

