For HCP Safety Population, the number and percent of patients experiencing SAEs and AEs of interest collected on HCP questionnaire during the HCP process will be tabulated by body system and MedDRA preferred term.

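### The HCP Safety Population is defined by consent alone, so consenting patients with no completed questionnaire lower the event percentages in the separate HCP tabulation

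*Protocol*

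**What the plan says.** Protocol section 10.1 sets the membership rule. The patient has declined re-enrollment or discontinued for another reason, and must "consent to data release for the completion of a simplified HCP questionnaire in the direct to HCP process. This will be the population". Completing a form is the purpose of the consent, not a condition of entry. The section assigns the set its use in these words: "This will be the population for safety analyses of data collected on HCP questionnaire".

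Section 10.5 fixes the statistic: "the number and percent of patients experiencing SAEs and AEs of interest collected on HCP questionnaire during the HCP process will be tabulated". No confidence interval and no patient-year rate is named for this population.

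Section 9.2 describes how data arrive. Forms are generated for consenting patients, and "Completed questionnaires will be entered into the database on an annual basis".

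Section 6.0 says who fills them in: "The questionnaire may be completed by the registry physician or the patient's current HCP", the latter when the patient has left the registry physician's care. On the status of that provider it adds, in part: "An HCP is not considered a participating investigator in the registry since they are only completing an annual questionnaire on behalf of a former registry".

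**The concern.** The denominator is fixed by consent, but the numerator can be filled only from completed questionnaires. A patient who consents and for whom no form comes back has no questionnaire data, yet counts in the percentage exactly like a patient observed to be free of events.

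Such patients are foreseeable. They have already left the Registry, and the form may fall to a provider who is not an investigator. Section 6.5 itself plans for patients who cannot be reached, but no rule removes them from the HCP denominator.

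Long-term safety is the primary objective (section 5.0), and section 4.0 says follow-up after discontinuation was added to obtain as much safety information as possible. A table from that process that reads lower as more patients have no form works against this purpose. Because some HCP patients are no longer on Humira, what is understated is the frequency of events after leaving the Registry.

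**Working it through.** **No plan figure to reproduce.** The protocol states no HCP population size, return rate or event percentage. The check is therefore a comparison of rules followed by algebra with assumed values.

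**Rules compared.**
- HCP Safety Population (10.1): discontinued or declined re-enrollment, plus consent. No data requirement.
- Episodic Dosing Population (10.1): must provide data before and after the interruption. The same section thus imposes a data requirement elsewhere.
- Registry Safety Population (10.5): percentages and rates per 100 patient-years, both with 95% confidence intervals. For the HCP population only number and percent are named, so no stated person-time measure offsets the denominator.

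**Inputs (all assumed).** N = consenting patients; r = share with at least one completed form; p = event risk in that share; m = risk in patients with no form relative to those with one. Patients with a form are taken as fully captured, so that partly returned series are set aside.

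**Formulas.**
- Reported percent = (N × r × p) / N = r × p
- True percent = p × [r + (1 − r) × m]
- Reported / true = r / [r + (1 − r) × m]

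**Results, reported / true.**

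| r | m = 0.5 | m = 1 | m = 2 |
|---|---|---|---|
| 0.9 | 0.9/0.95 = 0.947 | 0.9/1.0 = 0.900 | 0.9/1.1 = 0.818 |
| 0.7 | 0.7/0.85 = 0.824 | 0.7/1.0 = 0.700 | 0.7/1.3 = 0.538 |
| 0.6 | 0.6/0.8 = 0.750 | 0.6/1.0 = 0.600 | 0.6/1.4 = 0.429 |

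At m = 1 a true 10% is reported as 10% × 0.9 = 9% or 10% × 0.6 = 6%. The ratio is below 1 whenever r < 1 and m > 0. It equals 1 only if every consenter has a form (r = 1) or those without one have no events (m = 0).

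**Check of the remedy.** With the denominator restricted to patients with a form, the reported percent is p, and p / true = 1 / [r + (1 − r) × m]. At r = 0.7 this is 1/0.85 = 1.176 for m = 0.5, 1.000 for m = 1, and 1/1.3 = 0.769 for m = 2. The relative error is (1 − r) × m / [r + (1 − r)m] in size on the consent denominator and (1 − r) × |1 − m| / [r + (1 − r)m] on the restricted one. The restricted denominator is nearer the truth when |1 − m| < m, that is, when m > 0.5. At m = 0.5 the two are equally far off (0.824 and 1.176 at r = 0.7).

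**The case against.** The strongest reply is that nothing in the protocol says patients without a form are counted as event-free. Sections 10.1 and 10.5 both speak of data collected on the questionnaire, and the exact table denominator could be left to the SAP, which is not at hand. This does not remove the point. The protocol states both the population and the percentage, and an SAP that required a form would be departing from the definition in 10.1.

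Several other replies stand as limits:
- The registry physician obtains the consent and may complete the form. The first form looks back from discontinuation to the start of the HCP process. Both may keep the group with no form small.
- Section 6.5 plans to match patients lost to follow-up against death, cancer and vital registries where allowed. These patients are therefore not wholly unobserved, although such data would not enter a questionnaire numerator.
- The HCP table is descriptive, with no test or comparator. Section 10.5 also tabulates HCP-process events together with all other events through last contact.

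A reader might infer that every missing form makes Humira look safer. The documents do not support that. Only patients with no form at all are affected by this mechanism; a patient with some forms missing raises a separate question of follow-up time. Some HCP patients are also off Humira. A reader might likewise infer that the main safety results are biased, but the Registry Safety Population does not use this denominator.

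**Conclusion.** The point holds for the separate HCP tabulation. Read as written, sections 10.1 and 10.5 place consenting patients with no completed questionnaire in the denominator and bar them from the numerator. The direction is certain if any such patient exists and has non-zero risk: the percentages are too low.

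The size is unknown. For an assumed 60% to 90% of consenters with at least one form, the reported percentage is 0.6 to 0.9 of the true one if non-returners carry equal risk. It is closer to the truth if their risk is lower, and further from it if their risk is higher. All values of r and m are assumptions.

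The Registry Safety Population percentages, the rates per 100 patient-years given for it and the sample size do not change. This is a real flaw in a secondary safety table, worth correcting because the correction is cheap.

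**What to change.** In section 10.1, define the HCP analysis set as consenting patients with at least one completed HCP questionnaire. In section 10.5, report beside the HCP table the number who consented, the number with at least one form, and forms expected against forms received.

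The cost is one clause in 10.1 and one line in the table. The stated population becomes smaller, and that is not the only downside. If return is related to risk, the restricted percentage is itself selected and may err either way, as the check of the remedy shows. The added counts do not remove that selection, but they let a reader judge how much room there is for it. Incomplete series of forms need their own treatment as a matter of follow-up time, and this change does not address them.

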10.2 Planned Methods of Statistical Analysis

Descriptive statistics are to be provided for demographic, effectiveness, and safety parameters. Continuous variables will be summarized by the number of observations, mean, standard deviation, 1st quartile, median, 3rd quartile, minimum, and maximum; whereas discrete variables will be summarized by counts and percentages. All analyses

will be performed on the Safety Population in the Registry that includes all patients who receive at least one dose of adalimumab unless otherwise specified.

10.3 Demographics and Registry Enrollment Characteristics

Demographic and Registry enrollment characteristics will be summarized.

The following covariates will be measured to assess their influence on the primary and secondary endpoints: age (years), sex, race/ethnicity, smoking history, duration of CD, severity of CD (as measured by Physician Global Assessment, WPAI and SIBDQ), prior therapies for CD, concomitant CD medications, co-morbid conditions, and adalimumab dosage and exposure duration.

10.4 Effectiveness Analyses

Effectiveness parameters measured over the course of registry, include change from registry enrollment in the following measures: SIBDQ, Health Care Resource Utilization, WPAI, and Physician's Global Assessment.

The Physician's Global Assessment and SIBDQ scores will be summarized descriptively at each Registry visit. Additionally, changes from Registry enrollment by Registry visit will also be summarized for these outcomes using descriptive statistics. Health Resource Utilization and WPAI will also be summarized with descriptive statistics at each Registry visit.

For efficacy analyses of the "episodic dosing" population, only patients providing evaluations of efficacy at the two timepoints described below will be considered:

- data prior to the interruption in dosing, specifically at/after 12 weeks from enrollment in the Registry study.
- data after the dosing interruption is over, specifically, at/after 12 weeks upon resumption of Humira. For these patients, efficacy data at/after 12 weeks of

the 1st treatment in the Registry and at/after 12 weeks after the restart of Humira treatment during the Registry study will be summarized.

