6.0 Investigational Plan

This is a multicenter, uncontrolled non-interventional Registry of patients with CD treated in a routine clinical setting with Humira. Approximately 5,000 subjects in the US, Europe, Canada, Australia, New Zealand and South Africa will be enrolled.

Physicians will be provided with a study kit that includes a protocol, patient informed consent forms, Serious Adverse Event Report Forms, paper patient questionnaires, and electronic Case Report Forms (eCRFs).

The decision to prescribe Humira (adalimumab) to the patients should be made separately from the decision to enroll them in the Registry.

With patient consent and having met all the inclusion criteria and none of the exclusion criteria, the physician may enroll the patient into the Registry. Physicians are encouraged to treat their patients as they would in their routine clinical practice and in accordance with the local Humira (adalimumab) product label. The physician will then follow the patient during regular office visits at intervals as determined by routine clinical practice or as recommended by national guidelines.

Patient's safety data and information about medications taken for CD will be recorded on eCRFs at study enrollment and during their regularly scheduled visits which are closest to Months 3, 6, 9, 12, 18, 24, 30, 36, 42, 48, 54, 60, 66 and 72. While the physician may deem it appropriate and necessary to have the patient return for intermediate visits during the course of the registry, data will be collected via eCRFs only at the intervals that most closely correspond to those described above.

In an effort to maximize safety data collection, physicians will be asked to do the following:

- Consent and re-enroll patients that were previously discontinued due to the prior P06-134 protocol withdrawal criteria (e.g., patient discontinued Humira). Patients that re-enroll in the Registry will resume data collection via the eCRF process as outlined in the protocol.
- For patients that re-enroll in the Registry, physicians will be asked to collect and report surgeries or hospitalizations and adverse events of special interest (Section 7.1.2) and Crohn's related medication use between registry discontinuation and re-enrollment based on a retrospective review of their patient records.

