6.4 Study Procedures

The following procedures will be performed during the study at the time points specified in [Table 1](#), Schedule of Study Assessments.

Table 1. Schedule of Study Assessments

Procedure	Study Enrollment	Month^a 3, 6, 9, 12, 18, 24, 30, 36, 42, 48, 54, 60, 66 and 72	At Time of Reported Event
Informed Consent	√		
Demographics	√		
Medical/Surgical Hx (including Crohn's Medical/Surgical Hx)	√		
Safety Data Collection (AEs of Interest/SAEs)	√	√	√
Previous Crohn's Disease Medications, prior concomitant medications	√		
Prior and Concomitant CD Medications	√	√	√
All Concomitant Medications	√		√
Physician Global Assessment	√	√	
SIBDQ	√	√	
WPAI (Work Productivity Activity Impairment) Questionnaire	√	√	
Healthcare Resource Utilization (Unscheduled Outpatient Visits, Emergency Room Visits and Hospitalizations Questionnaire)	√	√	
Adalimumab Treatment and Dosing Changes	√	√	
Case Report Form Completion	√	√	√

a. Data collection at regular visits that are closest to time points described. For patients participating in the HCP questionnaire process, follow-up is annually and events of interest, surgeries, hospitalizations and medications taken for CD are collected.

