6.4.7 Outcomes and Questionnaires

The patient will complete the SIBDQ and WPAI Questionnaires at all study visits starting at Registry enrollment, if part of the physician's routine clinical assessment. Patients will complete the questions directly on the eCRFs that will be considered source documents. A copy of the SIBDQ is located in [Appendix C](#). A copy of the WPAI is located in [Appendix E](#).

The Healthcare Resource Utilization form (Unscheduled Outpatient Visits, Emergency Room Visits and Hospitalizations Questionnaire) will be completed by site staff starting at

study enrollment, if part of the physician's routine clinical assessment. Only patients who have previously been enrolled in an adalimumab clinical trial will have this questionnaire completed at Registry Enrollment.

A copy of the questionnaire is located in [Appendix D](#).

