6. Overall, in the last 2 weeks, how much of a problem have you had with passing large amounts of gas? Please choose an option from (Bowel)
- A major problem
 - A big problem
 - A significant problem
 - Some trouble
 - A little trouble
 - Hardly any trouble
 - No trouble
7. Overall, in the last 2 weeks, how much of a problem have you had maintaining or getting to, the weight you would like to be at? Please choose an option from (Systemic)
-

- A major problem
 - A big problem
 - A significant problem
 - Some trouble
 - A little trouble
 - Hardly any trouble
 - No trouble
8. How often during the last 2 weeks have you felt relaxed and free of tension?
Please choose an option from (Emotional)
- None of the time
 - A little of the time
 - Some of the time
 - A good bit of the time
 - Most of the time
 - Almost all of the time
 - All of the time
9. How much of the time during the last 2 weeks have you been troubled by a feeling of having to go to the bathroom even though your bowels were empty? Please choose an option from (Bowel)
- All of the time
 - Most of the time
 - A good bit of the time
 - Some of the time
 - A little of the time

- Hardly any of the time
 - None of the time
10. How much of the time during the last 2 weeks have you felt angry as a result of your bowel problem? Please choose an option from (Emotional)
- All of the time
 - Most of the time
 - A good bit of the time
 - Some of the time
 - A little of the time
 - Hardly any of the time
 - None of the time

Appendix D. Health Care Resource Utilization (Unscheduled Outpatient Visits, Emergency Room Visits and Hospitalizations)

1. Since the last study visit has the subject had any physician/health care visits for their Crohn's disease other than the protocol visits?

No Yes (if yes provide the following)

Type of Visit	2. Number of Visits	3. Total Number of Days
Physician		
Emergency Room		
Hospital Admission		

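### Health care use is summarized by visit without a time denominator although the form's look-back doubles after Month 12; separately, its change from enrollment is undefined for patients with no earlier adalimumab trial

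*Protocol*

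**What the plan says.** **Summary planned.** Section 10.4 of the protocol states: "Health Resource Utilization and WPAI will also be summarized with descriptive statistics at each Registry visit". For continuous variables, section 10.2 defines the descriptive statistics: "Continuous variables will be summarized by the number of observations, mean, standard deviation, 1st quartile, median, 3rd quartile, minimum, and maximum". Discrete variables get counts and percentages. Neither section gives utilization a time denominator.

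**What the form counts.** Appendix D asks: "Since the last study visit has the subject had any physician/health care visits for their Crohn's disease other than the protocol visits". It then records the number of visits and the total days for physician, emergency room and hospital admission. The look-back is therefore the gap between visits, not a fixed period.

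**Schedule.** Section 6.0 sets the visits at "Months 3, 6, 9, 12, 18, 24, 30, 36, 42, 48, 54, 60, 66 and 72". The footnote to Table 1 adds: "Data collection at regular visits that are closest to time points described".

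**Change from enrollment.** The opening sentence of section 10.4 says the effectiveness parameters "include change from registry enrollment in the following measures: SIBDQ, Health Care Resource Utilization, WPAI" and the Physician's Global Assessment. Table 1 ticks the utilization form at enrollment with no restriction. Section 6.4.7 says: "Only patients who have previously been enrolled in an adalimumab clinical trial will have this questionnaire completed at Registry Enrollment".

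**The concern.** A count taken over a window grows with the window. If the window changes during follow-up and the count is tabulated by visit, the table mixes the rate of use with the length of the look-back. Here the scheduled look-back changes once, between Months 12 and 18. A reader of the by-visit table could take that step for a worsening of disease control, or miss a real improvement that it hides.

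The second matter is independent of the first. A change from enrollment needs an enrollment value. The protocol lists the change, shows the form at enrollment for everyone in one place, and limits it to a subgroup in another. Sites that follow Table 1 and sites that follow section 6.4.7 would collect different data.

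Utilization is one of the four effectiveness measures listed in section 10.4 for the secondary objective. It has no test and no comparator, so what is at stake is a correct description of use over time.

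**Working it through.** The protocol gives no expected figure for health care use, so there is none to reproduce. The check uses the schedule and the form.

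**Step 1: nominal windows.** Differences between successive visits, from enrollment to Month 72, are 3, 3, 3, 3 months, then 6 months ten times. In years, w = 0.25 through Month 12 and w = 0.50 from Month 18.

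**Step 2: mean count per visit.** With a constant rate r per patient-year, the expected count is r × w.
- Month 12: 0.25r
- Month 18: 0.50r
- Ratio: 0.50r / 0.25r = 2.00, whatever r is.

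Mean days scale in the same way if the average days per contact do not change. If one scheduled visit after Month 12 is missed, the next window is 12 months and the expected count is 1.0r.

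**Step 3: share of patients with any use.** Under a Poisson model this is 1 − exp(−r × w). The documents give no rate, so r is an assumption, taken from 0.05 to 1.0 per patient-year.

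| Assumed r | Month 12 | Month 18 | Ratio |
|---|---|---|---|
| 0.05 | 1.2% | 2.5% | 1.99 |
| 0.2 | 4.9% | 9.5% | 1.95 |
| 0.5 | 11.8% | 22.1% | 1.88 |
| 1.0 | 22.1% | 39.3% | 1.78 |

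**Step 4: what a real change would look like.** If the rate falls by a fraction d after Month 12, the apparent ratio of means is 2 × (1 − d).
- d = 0.3: 2 × 0.7 = 1.4, a true 30% fall shown as a 40% rise.
- d = 0.5: 2 × 0.5 = 1.0, a true 50% fall shown as no change.

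**Step 5: after scaling.** Dividing by the window gives 0.25r / 0.25 = r and 0.50r / 0.50 = r. The ratio is 1.00 at every assumed rate.

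**Step 6: actual windows.** Suppose each visit may fall anywhere nearer to its own time point than to its neighbours. The Month 9 visit then lies between 7.5 and 10.5 months, Month 12 between 10.5 and 15, and Month 18 between 15 and 21. The window at Month 12 could run up to 15 − 7.5 = 7.5 months, and at Month 18 up to 21 − 10.5 = 10.5 months. These are outer limits, but they show that nominal months would not be a safe denominator.

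**Step 7: who has an enrollment value.** Section 6.2.1 admits newly prescribed patients and patients already on commercial drug, as well as current and former trial participants. Under section 6.4.7, patients with no earlier adalimumab trial have no form at enrollment, so the change listed in section 10.4 cannot be computed for them. Under Table 1 they would have one. The two passages cannot both be followed.

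**The case against.** **The protocol never says raw counts.** This is correct. Section 10.4 does not define the utilization variable, and an analysis plan that is not shown could annualize it. A reader might infer that a false rise in hospitalizations is built into the registry. The text does not support that: the step follows only if section 10.4 is carried out as written, and it would affect physician and emergency visits as well as admissions. What remains is that section 10.4 chooses the visit as the unit for a variable-window count, while section 10.5 of the same protocol uses 100 patient-years for safety events.

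**The artefact is narrow.** This is also correct. It is one scheduled step. Nominal windows are equal among Months 3 to 12 and among Months 18 to 72. The factor of 2.0 is for means at a constant rate with visits on schedule; a real fall or selective dropout could offset it.

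**The change-from-enrollment point is loose wording.** This stands in part. The next paragraph of section 10.4 assigns change summaries only to the Physician's Global Assessment and SIBDQ. The opening list still names utilization, and the conflict between Table 1 and section 6.4.7 concerns data collection, which an analysis plan cannot repair afterwards. Two further inferences fail. A missing baseline makes a change undefined; it cannot create a rise. Nor does section 6.4.7 show that former trial patients' enrollment value reflects time on active drug, because it gives neither the look-back nor the treatment during it.

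**Hospital burden is reported elsewhere.** An adverse event leading to admission is an SAE under section 7.1.3, and SAEs are reported per 100 patient-years. This limits the consequence but does not correct the utilization table.

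**Conclusion.** Two separate defects hold. First, a by-visit summary without a time denominator, applied to a count since the last study visit, gives a spurious step between Months 12 and 18. It is 2.0-fold for the mean count and 1.78- to 1.99-fold for the share with any use. The mean result rests on a constant rate and visits at their nominal months. The share result also rests on a Poisson model and assumed rates of 1.0 to 0.05 per patient-year. Irregular visits add variation in either direction. Second, the change from enrollment listed for utilization is undefined under section 6.4.7 for every patient with no earlier adalimumab trial, and Table 1 contradicts that section.

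Both concern a secondary descriptive measure and deserve correction at that level. The primary safety rates are unaffected.

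**What to change.** - **Section 10.4, summary.** Report each utilization item as events, and days, per patient-year: total count divided by total actual time since the previous study visit. For the first post-enrollment form of patients with no earlier visit, count time from enrollment. The time should run from the previous visit and not from the previous completed form. The form looks back to the last visit and is completed only where it is part of routine assessment, so counting from the last form would overstate the time and bias the rate downward when a form was skipped. Leave out the person-time of windows with no form.
- **Section 10.4, change list.** Remove utilization from the change-from-enrollment measures, or restrict it to former adalimumab-trial participants and label it so. If it is kept, state the look-back of the enrollment form.
- **Table 1 and section 6.4.7.** Align them, for example with a footnote to the enrollment tick.

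The cost is a few sentences and a footnote, with no new assessment. The calculation needs the date of every study visit. Section 6.4.8 names the visit date explicitly for the enrollment eCRF, so the sponsor should confirm that it is also recorded at follow-up. Use in windows with no form stays unknown, and restricting the change analysis leaves it describing only a subgroup.
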